**8.1.7 Route of administration for this study:**

Intravenous infusion. Do not administer as an IV push or bolus injection. Administer through a 0.2 micron to 1.2 micron pore size, low-protein binding polyethersulfone membrane in-line filter.

At the end of the infusion period, flush the line with a sufficient quantity of approved diluents.

**8.1.8 Potential Drug Interactions:**

No incompatibilities between nivolumab injection and polyvinyl chloride (PVC), non-PVC/non-DEHP (di[2-ethylhexyl]phthalate) IV components, or glass bottles have been observed.

**8.1.9 Availability:**

The supply for this study will be investigational – not commercially available. Supply will be provided by BMS free of charge. Nivolumab will be supplied as 100 mg/vial (10mg/mL) packaged in cartons of 5 or 10

vials. Drug is protocol specific, but not patient specific.

Drug can be ordered using the Drug Request Form provided by BMS. The form is provided as a separate document and should be submitted electronically at least 7 business days for initial order and at least 14 days for re-supply before the expected delivery date. The initial order should be limited to 20 vials. Contact and submission details can be found directly on the Drug Request Form. Deliveries will be made Tuesday through Friday.

#### **8.1.12 Return and Retention of Study Drug**

The clinical study team will be responsible for keeping accurate records of the clinical supplies received from BMS or designee, the amount dispensed to and returned by the subjects and the amount remaining at the conclusion of the trial.

Upon completion or termination of the study, all unused and/or partially used investigational product will be destroyed at the site per institutional policy. It is the Investigator's responsibility to arrange for disposal of all empty containers, provided that procedures for proper disposal have been established according to applicable federal, state, local and institutional guidelines and procedures, and provided that appropriate records of disposal are kept.

#### **8.1.13 Side effects**

Local bladder toxicities including but not limited to dysuria, urinary urgency, frequency and hematuria. Immune-related adverse events have been associated with Nivolumab is administered intravenously.

Below are safety data from 268 subjects with unresectable or metastatic melanoma and 117 patients with metastatic squamous NSCLC who received nivolumab alone. Related side effects reported in subjects receiving nivolumab alone were:

**Very Frequent** – Expected to occur in more than 20% of people (more than 20 out of 100 people): Fatigue (50%), Dyspnea (38%), Musculoskeletal pain (36%), Rash (21%), Increased AST (28%), Increase alkaline phosphatase (22%), Hyponatremia (25-38%)

**Frequent** - Expected to occur in 10% to 20% of people (10 to 20 out of 100 people): Pruritus (19%), Cough (17%), URI (11%), Peripheral edema (10%), Increased ALT (16%), Hyperkalemia (15%)

**Not Frequent** – Expected to occur in less than 10% of people (less than 10 out of 100 people): ventricular arrhythmia, iridocyclitis, infusion-related reactions, increased amylase, increased lipase, dizziness, peripheral and sensory neuropathy, exfoliative dermatitis, erythema multiforme, vitiligo, psoriasis

Deaths thought to be related to nivolumab when given alone were reported in approximately 0.5% of subjects treated (approximately 1 out 200 people).

For the most recent safety update, please refer to the current Investigator's Brochure or Study Agent Prescribing Information.

## **9.0 CORRELATIVES/SPECIAL STUDIES**

### **9.1 Tumor biopsy immunohistochemical (IHC) staining and analysis for PD-L1, PD-1, CD8+ and CD4+ tumor infiltrating lymphocytes**

Detection of the selected markers for this study will be performed using immunohistochemistry. After the staining, the slides will be digitally scanned in an Aperio AT system (Aperio™, Leica Biosystems™) to convert the IHC slides into digital pathology files for posterior analysis. IHC expression analyses of markers consider a thorough staining pattern evaluation including distribution (percentage of positive cells) and intensity in the form of H-score, and evaluating the IHC expression in the proper subcellular location (i.e. membrane, cytoplasm or nucleus). IHC analysis and scoring will be performed by a certified pathologist using an image analysis software (Image Toolbox, Aperio™).

Outcome from the analysis will be calculated according to the H-score. The H-score ranges from 0 to 300, and it considers both intensity of the IHC (from 0 to 3) and distribution (percentage of the target cells positive, from 0 to 100). The scoring is the addition of the percentages of cells with intensity 0 + intensity 2 + intensity 3, thus the addition of the final percentage is 100% and the scoring will range from 0 to 300. Hence, the H score will incorporate both percentage of positive cells and intensity of marker expression. Hematoxylin/eosin and PD-1, PD-L1 and PD-L2-stained sections will be reviewed by a pathologist. Criteria to be evaluated include histologic subtype and grade, TNM 2002 pathologic tumor stage, the presence and type of intratumoral lymphocytic infiltration, and the quantity and location of PD-L1 staining. The tumor will be considered positive for PD-1, PD- L1, PD-L2 if >5% of tumor cells had histologic evidence of plasma membrane staining.

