## 1.4 Exploratory Studies

### **To explore the correlation between PD-1, PD-L1 and PD-L2 expression and CD4+ and CD8+ tumor infiltrating lymphocytes and PFS, OS and response to treatment.**

PD-1 is a key immune checkpoint receptor expressed by activated T cells and mediates immunosuppression. PD-1 functions primarily in peripheral tissues, where T cells may encounter the immunosuppressive PD-1 ligands PD-L1 and PDL-2, which are expressed by tumor cells, stromal cells or both [46-48]. PD-L1 and PD-L2 are overexpressed in a variety of solid tumors however no data exists in ACC [46].

There are conflicting data on the predictive value of PD-L1 expression on PD-1 directed therapy in solid tumors [36, 46]. Herbst et al showed that patients with solid tumors including non-small cell lung cancer and melanoma treated with humanized PD-L1 antibody had higher ORR when immunohistochemistry showed intense staining for PD-L1 in the tumor [49]. The same correlation was not observed on stratified analysis according to tumor cell membrane PD-L1

expression of non-small cell lung cancer patients treated with nivolumab therapy in the second line setting [36].

Pathological slides from tumor archival tissue will be stained using a monoclonal antibody against PD-L1 and defined as PD-L1 positive if equal or greater than 5% of the tumor cells membrane analyzed. We hypothesize that tumor cell membrane expression of PD-L1 or PD-L2 can have an impact on treatment responses.

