### 2.3 Exploratory Objectives & Endpoints

- 2.3.1 To assess the overall response rate, progression free survival and overall survival according to tumor PD-L1 and PD-L2 expression,
- 2.3.2 To assess the overall response rate, progression free survival and overall survival according to serum interleukin levels and peripheral T cell profile levels,
- 2.3.3 To measure humoral and cellular responses to tumor antigens on serum samples by measuring the levels of cytokines (ie, IL-2, IL-6, IL-8, IL-10, IL-18, IFN $\gamma$  and TNF- $\alpha$ ) and peripheral blood lymphocyte phenotype. We will explore potential correlations between differential measures of response and the toxicity and efficacy of nivolumab,

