-  Serum or urine test for females of child-bearing potential must be completed at screening and within 24 hours of treatment.
-  Nivolumab will be administered IV at 240mg over 30 minutes every two weeks.
-  A correlative blood sample will be drawn pre-dose at C1D1 and C2D15. Please see separate lab manual for details.
-  Archival tissue will be collected at baseline if available. Please see separate lab manual for details.
-  Treatment will continue until confirmed disease progression, unacceptable toxicity, or withdrawal of consent. Study assessments may take place within 24 hours of scheduled treatment if needed.
-  End of Treatment visit will occur approximately 12 weeks after stopping nivolumab treatment, or until the patient starts new treatment, whichever occurs first.
-  Patients will be followed (either by routine clinic visit or by phone) every 2 weeks while on treatment and every 3 months for up to 2 years while off treatment to document survival and disease progression. Adverse events will be followed for the first 12 weeks after stopping treatment.

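### The H-score formula in section 9.1 has no intensity weights and cannot give the 0 to 300 range stated beside it

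*Combined protocol and SAP*

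**What the plan says.** Section 9.1 makes the H-score the outcome of the immunohistochemistry analysis. It describes the score this way: "The H-score ranges from 0 to 300, and it considers both intensity of the IHC (from 0 to 3) and distribution", the distribution being the percentage of target cells that stain. The rule for computing it follows: "The scoring is the addition of the percentages of cells with intensity 0 + intensity 2 + intensity 3", and the sentence ends "thus the addition of the final percentage is 100% and the scoring will range from 0 to 300". The section then says the score is meant to reflect both how many cells stain and how strongly.

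Section 9.1 also gives a separate yes/no class: a tumour is positive for PD-1, PD-L1 or PD-L2 "if >5% of tumor cells had histologic evidence of plasma membrane staining". Section 1.4 words the PD-L1 class slightly differently: "defined as PD-L1 positive if equal or greater than 5% of the tumor cells membrane analyzed".

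The markers serve exploratory objective 2.3.1: "To assess the overall response rate, progression free survival and overall survival according to tumor PD-L1 and PD-L2 expression". That objective does not say whether expression means the H-score or the 5% class, and section 10.2 describes no marker analysis. On tissue, footnote 8 to the section 5.0 table says "Archival tissue will be collected at baseline if available".

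**The concern.** A sum of percentages drawn from one set of cells cannot exceed 100, so the printed rule cannot yield a score that reaches 300. The rule also omits intensity 1, includes the negative cells, and attaches no weight to any level.

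The result is more than a change of scale. Followed literally, the rule gives a completely negative tumour and a uniformly strong one the same score, and gives the lowest score to a uniformly weak tumour. An exploratory analysis relating such a score to response, PFS or OS would use a variable that does not measure expression. Section 9.1 is also the only scoring rule in these documents, so nothing else in them corrects it.

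**Working it through.** **Inputs, all from section 9.1.** Intensity levels are 0, 1, 2 and 3. Write P0, P1, P2 and P3 for the percentages of cells at each level, so P0 + P1 + P2 + P3 = 100. The stated range of the score is 0 to 300.

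**Attempt to reproduce the stated range from the printed rule.**

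Printed score = P0 + P2 + P3 = 100 − P1.

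The minimum is 0 (P1 = 100) and the maximum is 100 (P1 = 0). The 0 to 300 range is not reproduced. Enumerating every whole-percent split gives the same limits.

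**Could a small slip explain it?** Five readings were compared. The column headed 90/10 is a tumour with 90% negative and 10% weak (1+) cells.

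| Reading | Formula | All negative | All 1+ | All 2+ | All 3+ | 90/10 | Range |
|---|---|---|---|---|---|---|---|
| A. As printed | P0 + P2 + P3 | 100 | 0 | 100 | 100 | 90 | 0 to 100 |
| B. Intensity 1 restored, no weights | P0 + P1 + P2 + P3 | 100 | 100 | 100 | 100 | 100 | always 100 |
| C. Intensity 1 in place of 0, no weights | P1 + P2 + P3 | 0 | 100 | 100 | 100 | 10 | 0 to 100 |
| D. Listed levels, weighted by intensity | 0×P0 + 2×P2 + 3×P3 | 0 | 0 | 200 | 300 | 0 | 0 to 300 |
| E. All levels, weighted by intensity | 1×P1 + 2×P2 + 3×P3 | 0 | 100 | 200 | 300 | 10 | 0 to 300 |

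- **B** fits the remark that the percentages add to 100%, so intensity 1 may simply have dropped out of the list. But a score that is 100 for every tumour carries no information.
- **C** is just the percentage of positive cells. It ignores intensity and stops at 100.
- **D** reaches 300 but treats 1+ cells as negative, so it falls below E by P1, anywhere from 0 to 100 points. Its three listed percentages also fail to add to 100% whenever 1+ cells are present.
- **E** reaches 300, counts every positive level and orders the four uniform tumours correctly.

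No unweighted reading exceeds 100. Both readings that reach 300 need weights that the text does not give.

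**What does not depend on the score.** The 5% class is a cell percentage set against a cut-off and does not use the formula. The two-stage rule (0 of 10, then 3 of 29) depends only on response counts. Its exact figures are a type I error of 0.047, power of 0.801 and an early-termination probability at a 5% response rate of 0.95^10 = 0.599, in line with the 5%, 80% and 60% in section 10.1.

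**The case against.** The strongest reply is that this is a proofreading slip that the paragraph corrects for itself. Section 9.1 names the H-score, gives the 0 to 300 range before and after the faulty sentence, and gives the intensity scale. It assigns scoring to a certified pathologist with image-analysis software, who is unlikely to give a negative tumour a score of 100. Under reading D the range is not contradicted at all, and the error is the missing intensity 1. Section 5.0 also refers to a separate lab manual, which is not among these documents. No decision in the trial turns on the score.

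Much of this stands as a limit on consequence: the intended score can probably be inferred, and the work is exploratory. It is also fair that the range alone does not settle the formula, since D and E both give 0 to 300. The sponsor should therefore confirm E.

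It does not clear the sentence. Reading D also relies on unprinted weights, and it gives no credit to weak staining in a score meant to reflect the percentage of positive cells. The lab manual is cited for sample and tissue collection, not for scoring. A reader who applies section 9.1 as written gets a wrong marker variable.

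**Conclusion.** The concern holds: the H-score rule is wrong as written. It equals 100 − P1, ranges from 0 to 100, and contradicts the range in its own paragraph. The essential defect is the missing weights, because restoring or substituting intensity 1 without them still does not give 0 to 300.

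The consequence is narrow. It reaches only exploratory analyses that use the H-score, in at most 33 patients and only those whose archival tissue is available. Whether objective 2.3.1 is among those analyses cannot be told from the documents. Primary response rate, sample size, error rates, PFS, OS, safety and the 5% class are unaffected. The correction should be made, but it has no bearing on the trial's main conclusions.

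The arithmetic assumes only that every scored cell falls in exactly one of the four levels. That formula E is the intended score is an inference from the stated intensity scale and range.

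**What to change.** In section 9.1, replace the scoring sentence with H = 1 × %(1+) + 2 × %(2+) + 3 × %(3+), where intensity 0 contributes nothing and the range is 0 to 300. The sponsor should confirm that this is the score the laboratory computes.

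In objective 2.3.1, state whether the analysis variable is the H-score or the 5% class.

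As a side matter, use one positivity cut-off: section 1.4 has at least 5% and section 9.1 has more than 5%. This matters only for a tumour read at exactly 5%.

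The cost is one sentence, a few words and one symbol. No new assay, samples or patients are needed.

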## 1.2 Intervention Overview & Background

### 1.2.1 Overview

Nivolumab (BMS-936558, MDX-1106) is a fully human monoclonal immunoglobulin G4 (IgG4) antibody (HunMab) that is specific for human programmed death-1 (PD-1, cluster of differentiation 279 [cd279]) cell surface membrane receptor (Investigator Brochure version 2014). PD-1 is a negative regulatory molecule that is expressed transiently following T-cell activation and on chronically stimulated T cells characterized by an “exhausted” phenotype. Nivolumab anti-tumor activity has been investigated in patients with melanoma, non-small cell lung cancer (NSCLC), and renal cell carcinoma (RCC). The combination of nivolumab and ipilimumab (anticytotoxic T lymphocyte associated antigen-4 [anti-CTLA-4]) in phase 1/2 trial showed markedly enhanced clinical activity with acceptable safety profile in melanoma patients [26].

The clinical use of monoclonal antibodies to T-cell inhibitory receptors has provided transformative information on the nature of the immune system and cancer. An emerging picture suggests that endogenous immune responses can mediate effective tumor regression and/or improved survival even in patients with large volume tumors resistant to other forms of therapy. Some of the unique features of this type of therapy, based largely on experience in advanced melanoma, include: improved overall survival (OS) with or without radiographic responses or improved progression-free survival (PFS); responses that may be delayed or occur after radiographic disease progression; combinations of immune modulators with enhanced or novel activities (in the example of ipilimumab and nivolumab); and toxicity that is almost exclusively immune or inflammatory in nature. It is not yet clear what factors determine responses and which components of the immune system are needed for this to occur. It seems likely that both memory helper and effector cells would be needed to sustain long-term responses. Increasing emphasis has been placed on understanding the relationships of the tumor, cellular infiltrate, and immunologic milieu surrounding each tumor.

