PD-1, a 55-kDa type 1 transmembrane protein, is a member of the CD28 family of T-cell co-stimulatory receptors that include Ig super family member CD28, CTLA-4, inducible co-stimulator (ICOS), and B and T lymphocyte attenuator (BTLA) (Investigator Brochure version 2014). PD-1 is transiently but highly expressed on activated T cells functioning to limit immune effectors at the site of activation. Chronic stimulation may prevent the re-methylation of the PD-1 gene leading to continuous expression and characterizes a state of “exhausted” T cells that lose function and proliferative capacity while enhancing a suppressive tumor microenvironment. PD-1 may act together with other T-cell modulating molecules, including CTLA-4, TIM-3, lymphocyte-activation gene 3 (LAG-3) as well as indoleamine-pyrrole 2, 3-dioxygenase 1 (IDO-1), cytokines, and transforming growth factor beta (TGF-beta).

Two ligands specific for PD-1 have been identified: PD-ligand 1 (PD-L1, also known as B7-H1 or CD274, expressed on tumor, antigen-presenting cells [APCs], and dendritic cells [DCs]) and PD-L2 (also known as B7-DC or CD273, expressed on endothelial cells). The interaction of PD-1 with PD-L1 and PD-L2 results in negative regulatory stimuli that down-

modulate the activated T-cell immune response through SHP-1 phosphatase.

PD-1 knockout mice develop strain-specific lupus-like glomerulonephritis (C57BL/6) and cardiomyopathy (BALB/c). In transplantable tumor models that expressed PD-1 and LAG-3 on tumor-infiltrating CD4+ and CD8+ T cells dual anti-LAG-3/anti-PD-1 antibody treatment cured most mice of established tumors that were largely resistant to single antibody treatment [27]. Despite minimal immunopathologic sequelae in PD-1 and LAG-3 single knockout mice, dual knockout mice abrogated self-tolerance with resultant autoimmune infiltrates in multiple organs, leading to eventual lethality.

PD-L1 expression is found on a number of tumors, and is associated with poor prognoses based on OS in many tumors, including melanoma, renal, esophageal, gastric, ovarian, pancreatic, lung, and other cancers (Investigator Brochure version 2014) [28-34]. No published data is available evaluating PD-L1 expression in adrenocortical carcinoma.

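### Section 9.1 calls PD-1 status from tumour cells, although the protocol places PD-1 on T cells, so the exploratory PD-1 label does not reflect the infiltrate

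*Combined protocol and SAP*

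**What the plan says.** Section 1.4 announces the analysis in its heading: "To explore the correlation between PD-1, PD-L1 and PD-L2 expression and CD4+ and CD8+ tumor infiltrating lymphocytes and PFS, OS and response to treatment". Section 9.1 describes the staining, digital scanning and scoring, and gives one binary rule for all three PD markers: "The tumor will be considered positive for PD-1, PD- L1, PD-L2 if >5% of tumor cells had histologic evidence of plasma membrane staining". The same section also says: "Outcome from the analysis will be calculated according to the H-score".

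On where the receptor sits, the protocol is consistent:

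- Section 1.2.1 describes PD-1 as "expressed transiently following T-cell activation and on chronically stimulated T cells", and again: "PD-1 is transiently but highly expressed on activated T cells functioning to limit immune effectors at the site of activation".
- For the mouse tumour models, Section 1.2.1 refers to tumours that "expressed PD-1 and LAG-3 on tumor-infiltrating CD4+ and CD8+ T cells".
- Section 1.4 states: "PD-1 is a key immune checkpoint receptor expressed by activated T cells and mediates immunosuppression".

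For the ligands, Section 1.4 speaks of the "PD-1 ligands PD-L1 and PDL-2, which are expressed by tumor cells, stromal cells or both". Section 1.2.1 is narrower on PD-L2, naming endothelial cells, but that does not bear on PD-1.

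Objective 2.3.1, the formal exploratory objective on tissue expression, names PD-L1 and PD-L2 and leaves PD-1 out.

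**The concern.** A cut-off on the share of tumour cells with membrane staining suits a molecule carried by tumour cells. Elsewhere the protocol uses the 5% tumour-cell threshold only for PD-L1: in Section 1.2.5 for a cited melanoma study, and in Section 1.4 for this trial's archival slides. The hypothesis in Section 1.4 concerns tumour-cell expression of the two ligands. Only Section 9.1 extends the threshold to PD-1, and it gives no reason.

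What is at stake is the meaning of the PD-1 label. If the exploratory correlation uses it, the result does not describe PD-1 on the infiltrating T cells, and a null finding would say nothing about them. Section 5.0 collects archival tissue only where it is available, from at most 33 patients, so there is little material to spend on a label that misses the intended cells.

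**Working it through.** The documents state no sample size, power or prevalence for the PD-1 analysis, so there is no planned figure to reproduce. The check is of the definition, followed by an illustration.

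**Step 1: cells counted against cells said to carry the marker.**

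| Marker | Cells counted for positivity (9.1) | Cells said to express it |
|---|---|---|
| PD-L1, PD-L2 | Tumour cells | Tumour cells, stromal cells or both (1.4) |
| PD-1 | Tumour cells | Activated or chronically stimulated T cells (1.2.1, 1.4); tumour-infiltrating CD4+ and CD8+ T cells in mouse models (1.2.1) |

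No section says that tumour cells, in this disease or any other, express PD-1. None says that they do not.

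**Step 2: the rule applied to three hypothetical tumours.**

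- A: many PD-1-positive lymphocytes, cancer cells unstained. Tumour cells positive = 0%, so PD-1 negative.
- B: no infiltrate, cancer cells unstained. Tumour cells positive = 0%, so PD-1 negative.
- C: no infiltrate, more than 5% of cancer cells stained. PD-1 positive.

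A and B differ in the feature that the protocol's biology points to, yet share a label. C, with no T cells, is the only positive.

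**Step 3: whether the H-score supplies another PD-1 readout.** Section 9.1 bases the score on the percentage of target cells that are positive but does not say which cells are the target for PD-1. It gives a range of 0 to 300. The sum as written adds the percentages at intensities 0, 2 and 3, omits intensity 1 and applies no weights. Those percentages are shares of the same cells, so the sum cannot exceed 100. A top value of 300 would need every cell at intensity 3 with weight 3 (3 × 100 = 300).

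**Step 4: effect on the correlation, as an illustration.** Assume 29 evaluable patients, all with tissue (a best case), and 4 responders, the success boundary in Section 10.1. Six responders are shown for comparison.

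- If PD-1 is only on T cells, positives = 0 of 29. One row of the two-by-two table is empty, no association can be estimated, and Fisher's exact p = 1.0 for any number of responders.
- If one tumour is positive and that patient responds, the smallest attainable p is 4/29 = 0.14 with 4 responders and 6/29 = 0.21 with 6.
- If two are positive and both respond, p = (4 × 3)/(29 × 28) = 0.015 with 4 responders and (6 × 5)/(29 × 28) = 0.037 with 6.

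The last case shows that a small p-value is possible if some tumour cells stain. It would still describe PD-1 on tumour cells, not on the infiltrate.

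**The case against.** The strongest reply is that the threshold sentence is not the only readout. Section 9.1 makes the H-score the outcome of the analysis, and its target cells could be lymphocytes for PD-1. The section also covers CD4+ and CD8+ infiltrating lymphocytes and has the pathologist note whether and what kind of lymphocytic infiltration is present, so tumours A and B would be told apart in the data. Slides are scanned and specimens banked, so PD-1 could be rescored later. Finally, objective 2.3.1 does not list PD-1, and any such correlation would be descriptive.

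Much of this stands. A reader might infer that the PD-1 correlation is unobtainable, or that PD-1-positive lymphocytes would never be counted. The documents do not support either: an H-score on lymphocytes is possible in principle, and the infiltrate is recorded. A reader might also infer that PD-1 positives would be close to none of the 33 patients. That is not a figure in the documents, which give no prevalence and never say that these tumour cells lack PD-1.

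The binary rule is not rescued. The H-score's target cell is unspecified for PD-1 and its formula does not match its range. Noting that lymphocytes are present does not say whether they carry PD-1, and the pathologist's criteria mention location of staining for PD-L1 only. Rescoring later would mean choosing the PD-1 measure after outcomes are known.

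**Conclusion.** The PD-1 positivity rule in Section 9.1 is wrong as written, and the error is confined to an exploratory analysis. The binary PD-1 status does not reflect PD-1 on infiltrating T cells, so a correlation with response, PFS or OS based on it would be uninformative. This rests on the protocol's own account of which cells express PD-1.

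The size depends on something the documents do not give. If PD-1 is confined to T cells, there are no positives and nothing can be estimated. If some tumour cells stain, there is a comparison, but of a different quantity. The mismatch holds in both cases.

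The primary response rate, sample size, error rates, and the main PFS, OS and safety analyses are untouched.

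**What to change.** - In Section 9.1, restrict the tumour-cell threshold to PD-L1 and PD-L2.
- Score PD-1 as the percentage of tumour-infiltrating lymphocytes that are positive, from the same scanned slides, and analyse it as a continuous value. No cut-off is then needed.
- Say how a tumour with no lymphocytes is handled, since the percentage then has no denominator. Reporting these tumours as a separate category is the simplest choice.
- Name lymphocytes as the H-score target cell for PD-1, and correct the formula so that it yields the stated range.
- Reconcile Section 1.4 with objective 2.3.1: either add PD-1 to the objective or drop it from Section 1.4. In the same edit, align the PD-L1 threshold, which includes exactly 5% in Section 1.4 and excludes it in Section 9.1.

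The cost is the wording and slightly more scoring work. Section 9.1 already plans PD-1 staining, scanning and a pathologist's reading with image-analysis software, so no new tissue or stain should be needed. This assumes that lymphocytes can be identified on the PD-1 slides, which the documents do not state. The change should be made before slides are scored against outcome.
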